8.3 Serious Adverse Events

An adverse event is any undesirable experience associated with the use of a medical product in a patient. The event is serious and reportable to the sponsor within 24 hours of knowledge of the event when the event was unanticipated or unexpected, or the patient outcome is any of the following, making the event “Serious”:

➤ Death

Report if you suspect that the death was an outcome of the adverse event, and include the date, if known.

➤ Life-threatening

Report if suspected that the patient was at substantial risk of dying at the time of the adverse event or use or continued use of the device or other medical product might have resulted in the death of the patient.

➤ Hospitalization (initial or prolonged)

Report if admission to the hospital or prolongation of hospitalization was a result of the adverse event.

Emergency room visits that do not result in admission to the hospital should be evaluated for one of the other serious outcomes (e.g., life-threatening, required intervention to prevent permanent impairment or damage, other serious medically important event).

➤ Disability or Permanent Damage

Report if the adverse event resulted in a substantial disruption of a person’s ability to conduct normal life functions, e.g., the adverse event resulted in a significant, persistent or permanent change, impairment, damage or disruption in the patient’s body function/structure, physical activities and/or quality of life.

➤ Congenital Anomaly/Birth Defect

Report if you suspect that exposure to a medical product prior to conception or during pregnancy may have resulted in an adverse outcome in the child.

➤ Required Intervention to Prevent Permanent Impairment or Damage (Devices)

Report if you believe that medical or surgical intervention was necessary to preclude permanent impairment of a body function, or prevent permanent damage to a body structure, either situation suspected to be because of the use of a medical product.

➤ Other Serious (Important Medical Events)

Report when the event does not fit the other outcomes but may jeopardize the patient and may require medical or surgical intervention (treatment) to prevent one of the other outcomes. Examples include allergic bronchospasm (a serious problem with breathing) requiring treatment in an emergency room, serious blood dyscrasias (blood disorders) or seizures/convulsions that do not result in hospitalization. The development of drug dependence or drug abuse would also be examples of important medical events.

8.5 Device Failures and Malfunctions

All reported device observations / performance issues, malfunctions, or failures of the NEUROMARK™ System are required to be documented in the CRF. In the event of a suspected observation or device problem (e.g., device failure or malfunction), the investigational device may need to be returned to the manufacturer for analysis. The site must contact the sponsor for instructions. Device failures and malfunctions will be documented in the Subject's study records. Should a return be required, general return instructions and supplies are included in the Study Binder.

NOTE: Device failures or malfunctions are NOT to be reported as adverse events. However, if there is an adverse event that results from a device failure or malfunction, that specific event would be recorded in the usual manner on the AE CRF.

9 PROTOCOL DEVIATIONS

Investigators must obtain prior approval from Neurent Medical and, in some cases where applicable, the reviewing IRB before initiating deviations from the protocol, except when necessary to protect the life or physical well-being of a Subject in an emergency. Such approval shall be documented in writing and maintained in clinical study management and Investigator files. Prior approval is generally not expected in situations where unforeseen circumstances are beyond the Investigator's control, (e.g., Subject was not available for scheduled evaluation, etc.); however, the event is still considered a deviation and will be reported on the appropriate CRF.

All deviations regardless of whether medically justifiable, pre-approved by Sponsor, or taken to protect the Subject in an emergency will be reported to the study Sponsor in a timely manner and documented in a Protocol Deviation CRF. Subject specific deviations will be reported on the Protocol Deviation CRF. Non-Subject specific deviations, (e.g. unauthorized use of an investigational device outside the study, unauthorized use of an investigational device by a clinician who has not signed an Investigator agreement or not been trained in the use of the device, etc.), will be reported to Sponsor. Investigators will also adhere to procedures for reporting study deviations to their IRB, in accordance with their specific IRB reporting policies and procedures.

Regulations require that Investigators maintain accurate, complete, and current records, including documents showing the dates of and reasons for each deviation from the protocol.

10 RISK – BENEFIT ASSESSMENT

Refer to risk-benefit details provided in **Appendix A**, the Investigator's Brochure. A summary overview is provided below in this section.

10.1 Potential Benefits

It is expected that the Neurent Medical NEUROMARK™ procedure may provide some benefit to the Subject; however, the actual benefits are not known. There may be no direct benefits of study participation.

A more-comprehensive Risk-Benefit assessment is included in the Investigator's Brochure provided as **Appendix A**.

10.2 Potential Risks

Refer to the manufacturer's labeling for details concerning potential AEs associated with the use of materials, tools or fluid used during the procedure or immediately post-procedure.

Potential risks to the study Subject that may be associated with the use of the NEUROMARK™ System are as follows. Risk of these events is low.

- Allergic or other reaction to device materials or anesthetic (subjects are to be excluded if an allergy/potential allergy is known)
- Trauma to the nasal cavity including

- Mucosal bleeding
 - Mucosal damage
 - Pain/discomfort
 - Synechiae/Adhesions
 - Perforation
- Infection
- Impaired Nasal Function including:
 - Olfactory change
 - Worsening nasal obstruction
 - Septal perforation
 - Worsened eustachian tube function
 - Cosmetic deformity
- Atrophic rhinitis or dry nose
- Headache
- Bone necrosis
- Burn

There may be additional risks related to the local anesthetic including dermal allergic reactions, itching, rash, erythema, stinging and inflammation. Many of these side effects will subside quickly. Systemic side effects are rare and unexpected. They include arrhythmia, hypotension, and a system allergic reaction.

There may be risks related to any post-procedure medication prescribed by the Study Investigator. Those risks can be found on the medication's labeling from the manufacturer.

10.3 Minimization of Anticipated Risks

Neurent Medical has received regulatory clearance for the NEUROMARK™ System in the USA under an FDA Class II device designation. The NEUROMARK System used in this clinical investigation is identical to the NEUROMARK System cleared by FDA. It is used in this study as an unaltered, commercially available medical device that is subject to Quality System Regulations and Good Manufacturing Practices per 21 CFR Part 820. Risks associated with the NEUROMARK™ System are minimized by design. Risks are minimized under this protocol due to:

- Only operators with proper training and experience will use the device
- Extensive non-clinical evaluation of the device (animal and bench-top testing)
- Clinical investigation in a non-therapeutic Clinical Study (non-active evaluation)
- The results of the RELIEVE Study (registry style first in human study) which indicates a positive safety profile
- The use of standard medical-grade materials in the manufacture of the device

11 STATISTICAL ANALYSIS

This is a prospective, single-arm, multicenter, safety and efficacy study.

Summary statistics will be calculated for endpoints and additional evaluations. Categorical variables will be summarized using frequency distributions and continuous variables will be summarized with means and standard deviations (normal distributions) or medians and ranges (non-normal distributions). Confidence intervals (95% CI) may be computed for select study measures.

Each subject serves as their own comparison of pre-procedure to post-procedure outcome scores. Primary efficacy will be assessed based on a reduction in the VAS Nasal Symptom Score as related specifically to rhinitis (rhinorrhea and nasal congestion) from pre-procedure [baseline] to 3 months post-procedure. The statistical methodology is targeted to employ the paired *t*-test and/or its nonparametric equivalent (the Wilcoxon Signed Rank test) with a 2-sided alpha level of 0.05. Additional Evaluations, as listed in the Protocol Synopsis, will be evaluated in a similar manner.

All subjects treated will be included in the safety analyses. All subjects treated who have at least one follow-up will be included in the efficacy analyses. All subjects treated will be included in the safety analyses.

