Study Endpoints:	
Safety will be evaluated based on frequency of Serious Adverse Events (SAEs) directly attributable to the NEUROMARK™ System at one (1) month post index procedure.
 
Efficacy will be assessed by the change in Visual Analog Scale (VAS) Nasal Symptom Score (NSS) from baseline through 3 months for rhinorrhea and nasal congestion.

Additional Evaluations:	
Additional information, as listed below, will be collected and the resulting data analyzed and reported for each follow-up, as applicable.
 
• A change in the VAS NSS from baseline.• A change in reflective Total Nasal Symptom Score (rTNSS) from baseline for rhinorrhea.• A change in rTNSS from baseline for nasal congestion.• A change in rTNSS from baseline.• A change in Postnasal Drip (PND) from baseline.• A change in Quality of Life (mini-Rhinoconjunctivitis Quality of Life Questionnaire (RQLQ) from baseline.• Procedure tolerability (e.g., discomfort, length of procedure)• Individual symptoms (e.g., post-nasal drip, nasal itching, sneezing)• Responder rates.• Patient satisfaction (e.g., patient reported symptom relief)• Endoscopic assessment.• Post-procedure discomfort (e.g., headache, facial pain, ear pain/blockage).• All adverse events regardless of severity or relatedness. 
All subjects who undergo treatment will be followed to 1 year for informational purposes and any study related findings will be reported.

Anticipated Duration:	
The study is anticipated to begin enrollment in Q1 of 2022 with enrollment complete in Q2 of 2022. The last patient visit is expected to take place by or during Q2 of 2023.

Study Evaluations:	Table 1 provides an overview of all protocol-related activities the Subject can expect to undergo as part of study participation.
Indications for Use	The NEUROMARK™ System is indicated for use in otorhinolaryngology (ENT) surgery for creation of radiofrequency (RF) lesions to disrupt posterior nasal nerves in patients with chronic rhinitis.
Intended Use:	The NEUROMARK™ System is intended for the application of Radiofrequency energy to create lesions in mucosal tissue in otolaryngological [also known as Ear, Nose and Throat (ENT)] procedures in patients with chronic rhinitis.

Screening Considerations:

- If data are available at baseline and the information collected per protocol, the existing data may be used to support patient screening. The test/assessment may not need to be redone.

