6.4 Follow-up evaluations

Subjects will undergo a brief evaluation at 24-48 hours following treatment. This follow-up evaluation may be performed over the phone or in-person.

The following procedures will be performed:

- Evaluation of procedure and anesthesia tolerability.
- Assessment for any adverse events.

- Review and collection of concomitant medications. Any changes to their medications will be documented.

Subjects will undergo additional follow-up evaluation at 1-month, 3-months, 6-months, 9-months and 1-year post treatment. It is preferred that subjects are seen in person; however, due to COVID-19 considerations, portions of the follow up that can be done remotely, may be performed using an online or by phone mechanism to obtain the necessary study data and information concerning the Subject's safety and well-being.

An overview of the evaluations in a checklist format is provided in **Table 1** above.

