11.2 Sample Size

It has been determined that treatment of 30 subjects is sufficient for assessing the safety and symptom reduction durability. To allow for up to 20% loss to follow-up, 36 subjects will be enrolled (treated) in the study.

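### Subjects with no 3-month VAS NSS are in the efficacy set but fall out of the primary paired test; no missing-data method is named, and the choice of test is left open

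*Combined protocol and SAP*

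**What the plan says.** - **Efficacy set (Section 11).** "All subjects treated who have at least one follow-up will be included in the efficacy analyses". Neither the visit nor the assessment that counts as a follow-up is specified.
- **Primary comparison (Section 11).** The reduction in VAS NSS for rhinorrhea and congestion is taken "from pre-procedure [baseline] to 3 months post-procedure". The synopsis words it as the change "from baseline through 3 months for rhinorrhea and nasal congestion".
- **Test (Section 11).** The method is described only as targeted: a paired t-test "and/or its nonparametric equivalent (the Wilcoxon Signed Rank test) with a 2-sided alpha level of 0.05".
- **First follow-up (Section 6.4).** "Subjects will undergo a brief evaluation at 24-48 hours following treatment. This follow-up evaluation may be performed over the phone or in-person". Table 1 schedules no VAS NSS at this contact; the first post-treatment score is at 1 month.
- **Expected loss (Section 11.2).** "To allow for up to 20% loss to follow-up, 36 subjects will be enrolled (treated) in the study". The time point to which the 20% applies is not stated.
- **Withdrawal (Section 6.5).** A subject may be withdrawn after starting a medication or treatment that the investigator thinks could distort the results.

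No section gives an imputation rule, a repeated-measures model or a sensitivity analysis for a missing 3-month score.

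**The concern.** The set is wider than the data that the primary test can use. A subject seen only at 1 month belongs to the efficacy set, but the 3-month paired test cannot use that score. A subject reached only by the 24-48 hour call belongs to the set with no outcome to analyse. Unless something fills the gap, the primary result describes the subjects who have a 3-month score.

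That matters if the missing subjects differ from the others. The Section 6.5 withdrawal reason makes this plausible, since subjects whose symptoms persist are the likelier ones to start another treatment. In a single-arm study there is no control group in which a similar bias could cancel. What is at stake is mainly the size of the reported improvement.

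Separately, no rule says which of the two tests is primary, so the choice could be made after both results are known.

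**Working it through.** **1. The plan's own figure.** 30 × 1.20 = 36, which matches Section 11.2. (30 / 0.80 = 37.5, rounded up to 38, is the other convention; the difference is a separate minor matter.) The base of 30 cannot be reproduced, because no effect size, SD or power is given.

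**2. How many subjects could be affected.** If the full 20% were lost by 3 months, 36 × 0.80 = 28.8, so 28-29 subjects would have a pair and about 7 could be in the set but outside the test. With 5% or 10% missing, 34.2 or 32.4 subjects would remain. As a plain illustration, if missing subjects had zero change, the mean over all 36 would be 29/36 = 0.81 of the observed-case mean with 7 missing, and 35/36 = 0.97 of it with 1 missing.

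**3. Bias of the observed-case mean.** All inputs here are assumptions: true change -4 at 3 months, SD 4, correlation r between the 1- and 3-month changes, and 1-month scores complete. Let z be the standardised 1-month change, with positive z a poorer response. The probability of a missing 3-month score is logistic(a + z), that is, a log-odds slope of 1 per SD, with a set to give the stated share missing. Then

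expected observed-case mean = -4 + r × 4 × E(z | observed),

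with E(z | observed) found by numerical integration.

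| Missing | a | E(z, observed) | r = 0.3 | r = 0.5 | r = 0.7 |
|---|---|---|---|---|---|
| 5% | -3.372 | -0.0471 | 1.4% | 2.4% | 3.3% |
| 10% | -2.564 | -0.0908 | 2.7% | 4.5% | 6.4% |
| 20% | -1.650 | -0.1732 | 5.2% | 8.7% | 12.1% |

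The last three columns give the overstatement. For the largest entry, 0.7 × 4 × 0.1732 = 0.485, so the expected mean is -4.48, and 0.485 / 4 = 12.1%. Because the assumed SD equals the assumed change, the percentage is simply r × |E(z)|; it shrinks if the true change is large relative to the SD.

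**4. Strength of dependence.** At r = 0.7 and 20% missing, simulated observed-case means were -4.26, -4.46, -4.64 and -4.72 as the slope rose from 0.5 to 2 per SD, so the overstatement reaches about 18% (0.72 / 4). With slope 0 there is no bias.

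**5. Using the 1-month score.** In the same simulations, the likelihood estimate that includes the 1-month score stayed at -3.98 to -4.00. Its standard error was 0.71-0.76, against 0.69-0.74 for the observed-case mean. The bias is removed at almost no cost in precision when missingness depends on the 1-month score.

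**6. Effect on the test.** With no true change, slope 1, r = 0.7 and 20% missing, the nominal 5% paired t-test rejects in about 9.5% of trials. With the assumed change of one SD, power is essentially 100% either way: 80% power needs a standardised change of only 0.55 at n = 28 or 0.48 at n = 36.

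**7. Open choice of test.** Reporting the smaller of the two p-values gave a type I error of about 5.3-6.7% across simulations with 28-36 subjects (normal and heavier-tailed changes).

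**The case against.** The best defence is that Section 11 defines the set for the efficacy analyses as a whole, not for the primary test alone. The synopsis has the additional evaluations, which include change in VAS NSS, reported for each follow-up, and Section 11 analyses them similarly. A subject with only a 1-month score therefore does enter an efficacy analysis, and the natural reading is available cases at each visit. This stands, and it rules out several stronger readings:

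- A reader might infer that the stated set and the stated test contradict each other. They do not. They coincide if every subject has a 3-month score; otherwise the plan is silent on how the gap is handled.
- A reader might infer that the 1-month score is discarded. It is analysed in its own right; it is only unused in the 3-month primary estimate.
- A reader might infer that the plan prescribes a completers analysis. It does not say so. Observed cases at 3 months are the default result of a paired test without imputation, and these are not the same as 1-year completers.
- A reader might take 20% as the 3-month loss. Section 11.2 does not tie it to 3 months, and follow-up runs to 1 year. Remote assessment (Section 6.4) and postponed visits (Screening Considerations) could keep the 3-month loss lower.

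On the tests, calling Wilcoxon the nonparametric equivalent, next to a normal/non-normal split, suggests a choice by distribution. That split formally governs descriptive summaries only, so the choice remains open, but the inflation is small.

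What the defence does not supply is any method for a missing 3-month score. The synopsis wording "from baseline through 3 months for rhinorrhea and nasal congestion" does not supply one either, because it names no way of using the 1-month result.

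**Conclusion.** The point holds as a gap in missing-data handling and test selection for the primary analysis. It should be fixed, but it does not threaten the feasibility of the study. The primary estimate defaults to 3-month observed cases and is biased towards benefit if poorer 1-month responders are more often missing at 3 months. Under the assumptions shown the overstatement is about 1-12%, rising to about 18% with the strongest dependence tried and falling to zero if dropout is random. None of the inputs (effect, SD, correlation, 3-month loss, dropout mechanism) is in the documents, so the range shows sensitivity and is not a forecast. A reader might infer that a positive test result would be unreliable. With a true change of the assumed size the test conclusion would not alter; inflation of the error rate matters only if the true change is near zero. The open choice of test adds about 0.3-1.7 percentage points to the 5% level.

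**What to change.** 1. Define the efficacy set as treated subjects with a baseline and at least one post-baseline VAS NSS. For the primary model this means a score at 1 or 3 months.
2. Make the primary analysis a likelihood-based repeated-measures model of change in VAS NSS at 1 and 3 months, with visit as a factor, mean-centred baseline as covariate, unstructured 2 × 2 covariance and Kenward-Roger degrees of freedom. Test the 3-month mean change at two-sided 0.05. Centring makes that mean well defined in a single arm. Two visits need 3 covariance parameters, against 15 for a five-visit unstructured model, which is more than 36 subjects need for a 3-month estimate.
3. Keep the paired t-test and the Wilcoxon test on observed 3-month data as named sensitivity analyses.
4. Add one sensitivity analysis that sets a missing 3-month change to zero.

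The cost is revised wording in Section 11 and slightly more analysis work, with no new data. The model relies on missingness depending only on observed scores; withdrawal after a new treatment may break that assumption, and the zero-change analysis probes it.

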11.1 Protocol Compliance

As with any clinical investigation, it is critical that one conduct the study per the Clinical Investigational Plan so that the study results are not compromised. Areas of particular criticality are as follows:

- Eligibility criteria (all patients treated must be eligible per the protocol)
- Patients should not be enrolled in another clinical study or be undergoing follow-up for another clinical study that may compromise study results
- Compliance with the protocol follow-up activity
- Thorough, accurate and timely reporting of adverse events
- Thorough, accurate and timely reporting of all clinical trial data

11.2 Sample Size

It has been determined that treatment of 30 subjects is sufficient for assessing the safety and symptom reduction durability. To allow for up to 20% loss to follow-up, 36 subjects will be enrolled (treated) in the study.

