1 PROTOCOL SYNOPSIS

Study Title:	Safety and Efficacy Study of the Neurent Medical NEUROMARK™ System in Subjects with Chronic Rhinitis
Short Title:	CLARITY Study
Study Device:	Neurent Medical's NEUROMARK™ System
Device Description:	
The NEUROMARK™ System is comprised of two (2) key devices; (1) a hand-held device designed to deliver Radio Frequency (RF) energy to soft tissue in otorhinolaryngological [also known as Ear, Nose and Throat (ENT)] procedures designed to interrupt nasal nerves aimed to reduce symptoms related to Chronic Rhinitis and (2) an algorithmically controlled low power radiofrequency Console (RFG) for delivery of RF energy to the device.
 
Refer to the Investigator's Brochure, provided as Appendix A, for additional details.

Study Objective:	The primary objective of this study is to evaluate the safety and efficacy of the Neurent Medical NEUROMARK™ System in patients that suffer from Chronic Rhinitis.
Study Design:	A prospective, single-arm, multicenter clinical Study to evaluate the safety and efficacy of the NEUROMARK™ System in patients with Chronic Rhinitis.
Study Size:	
This study aims to evaluate a total of thirty-six (36) study subjects at up to four (4) study centers. All subjects who meet the inclusion and exclusion criteria will receive treatment.
 
It is anticipated that approximately 15 subjects will be enrolled at each site. There is no enrollment maximum per site; however, no investigator may enroll more than 50% of the study population.

Subject Population:	Male and female patients in good general health who experience chronic rhinitis will undergo an initial screening. Those who provide written informed consent and meet eligibility criteria will be considered for enrollment.
Study Procedure:	Subjects that provide informed consent and meet study eligibility requirements will receive undergo treatment. Subjects will have the NEUROMARK™ System applied to both nostrils during a single session. The study procedure will be performed following the NEUROMARK™ System Instructions for Use (IFU), Appendix B .

Study Visits:	
All subjects will be evaluated at baseline, during treatment, immediately post-treatment, and at 24-48 hours, 1- month, 3- months, 6-months, 9-months and 1-year post treatment.
 
Refer to Table 1 for an overview of tests, procedures and other activities the subject will undergo as part of this clinical study.

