5 ENROLLMENT

Subjects will be considered enrolled once the informed consent is obtained, they meet the study eligibility criteria, and receive treatment.

If for some reason a Subject has consented, but becomes ineligible prior to enrollment, the reason for ineligibility will be documented on the Screening Log and the Subject consent document will be maintained in the site's study records.

Definition of Enrollment: Subjects will be considered enrolled once they are consented, meet eligibility criteria, and have received treatment.

At the time of enrollment, the Subject Sequence Number will be assigned to the Subject.

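### Section 11.2: a loss of up to 20% from 36 treated subjects can leave 29, one fewer than the 30 the plan calls sufficient

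*Combined protocol and SAP*

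**What the plan says.** The sizing statement is two sentences in Section 11.2. The first gives the target: "It has been determined that treatment of 30 subjects is sufficient for assessing the safety and symptom reduction durability". The second gives the number to be treated and the reason for the difference: "To allow for up to 20% loss to follow-up, 36 subjects will be enrolled (treated) in the study". The Study Size entry of the Protocol Synopsis repeats the total: "This study aims to evaluate a total of thirty-six (36) study subjects at up to four (4) study centers". Section 7 also plans for 36 devices, one per subject.

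Two other statements fix how the figures should be read. Section 5 defines enrollment: "Subjects will be considered enrolled once they are consented, meet eligibility criteria, and have received treatment". Section 11 defines who is analysed for efficacy: "All subjects treated who have at least one follow-up will be included in the efficacy analyses". Section 11 also names a paired t-test and/or the Wilcoxon signed rank test, "with a 2-sided alpha level of 0.05". No effect size, standard deviation, power or precision target is given for the 30.

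**The concern.** An allowance for loss to follow-up is meant to ensure that, if the stated loss occurs, the stated number of subjects is still there. Here it does not. A study that loses 7 of its 36 subjects stays within the tolerance in Section 11.2 and yet ends below the number the same section calls sufficient.

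What is at stake is mainly the coherence of the plan's only sizing statement. If 7 subjects are lost, the reader of the final report cannot tell whether the study met its plan: it did by the 20%, and it did not by the 30.

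**Working it through.** **Inputs.** Sufficient number: 30 (Section 11.2). Loss allowance: up to 20% (Section 11.2). Treated: 36 (Section 11.2, Synopsis, Section 7). Base of the loss: treated subjects, because Section 5 counts a subject as enrolled only after treatment.

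**Step 1: reproduce the 36.** Adding the loss to the target gives 30 x (1 + 0.20) = 36.0, exactly the stated figure. Dividing it out gives 30 / (1 - 0.20) = 37.5. The plan shows no formula, so the first route is an inference.

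**Step 2: apply the stated loss to 36.** 36 x 0.80 = 28.8. In whole subjects, 0.20 x 36 = 7.2, so at most 7 losses are within the allowance:

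| Lost of 36 | Loss | Remaining | Within 20%? | At least 30 left? |
|---|---|---|---|---|
| 6 | 16.7% | 30 | yes | yes |
| 7 | 19.4% | 29 | yes | no |
| 8 | 22.2% | 28 | no | no |

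The two statements conflict only in the row with 7 losses. The largest loss that 36 can carry is (36 - 30) / 36 = 16.7%.

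**Step 3: the smallest number treated that satisfies both statements.**

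| Treated | 20% of treated | Most losses allowed | Remaining |
|---|---|---|---|
| 36 | 7.2 | 7 | 29 |
| 37 | 7.4 | 7 | 30 |
| 38 | 7.6 | 7 | 31 |

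Rounding 37.5 up gives the textbook 38, but 37 already suffices in whole subjects.

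**Step 4: what one subject is worth.** This cannot be derived from the plan. As an illustration only, assume 80% power, two-sided alpha 0.05, a paired comparison and the normal approximation. The detectable standardized change is (1.960 + 0.842) / sqrt(n): 0.51 at n = 30 and 0.52 at n = 29. At 90% power the values are 0.59 and 0.60.

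**The case against.** The best defence has three parts.

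First, Section 11.2 speaks of treating 30 subjects and calls that number sufficient, not required. With 36 treated, the 30 is met on a literal reading. But loss to follow-up cannot reduce the number treated. If 30 meant only treated subjects, no allowance would be needed, so the second sentence makes sense only if 30 are meant to remain. It does stand that the plan does not call 30 a minimum or a number of completers.

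Second, the main endpoints are largely shielded. Safety is assessed at 1 month, in all treated subjects. Primary efficacy is at 3 months, and the efficacy set takes anyone with at least one follow-up. Later follow-up is described as informational: "All subjects who undergo treatment will be followed to 1 year for informational purposes and any study related findings will be reported". This stands in good part and places the shortfall mainly at the later visits. It does not remove the point. Section 11.2 names durability as a purpose of the 30, a paired test at any visit needs a score at that visit, and Section 11 gives no rule for missing scores.

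Third, one subject is trivial. As to size, that is right, and Step 4 agrees. It limits the weight of the point but does not make the two sentences consistent.

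A reader might also infer that the study is underpowered, or that it must recruit to 38. The documents support neither. With no power basis for the 30, no loss of power can be shown, and the inconsistency can be removed without treating anyone more.

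**Conclusion.** The inconsistency holds as written. Under the loss that Section 11.2 calls tolerable, 36 treated subjects can fall to 29, against a stated sufficient number of 30. The real tolerance is 6 of 36 (16.7%). No other section gives a different derivation or loss rate.

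The size is one subject in the worst permitted case. A reader who rounds 28.8 down might report 28, but that takes 8 losses, or 22.2%, which is outside the allowance.

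The conclusion rests on two readings: that the 20% is taken from treated subjects, which Section 5 supports, and that 30 are meant to remain after losses, which is the natural sense of the allowance but is not spelled out. It does not depend on how the sponsor reached 36. This is a minor correction and gives no ground to doubt the primary analysis.

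**What to change.** Keep the number treated at 36 and change the allowance in Section 11.2 to read, for example: *up to 6 of 36 subjects (16.7%) lost to follow-up*. The Synopsis and the device estimate in Section 7 then stand unchanged.

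Alternatively, keep the 20% and restate the number expected to remain as 29. This is equally consistent, but it alters the figure the plan calls sufficient, for which no basis is given, so the first option is cleaner.

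Either way the cost is an edit to Section 11.2. No subjects, visits or analyses are added. The only downside of the first option is a slightly less favourable stated allowance.
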